5.4.4 Dermatology/Skin Toxicities/Paronychia

The use of medications for the supportive care of rash is permitted, provided that compliance with Section 5.4 regarding concomitant medications is observed. Early initiation of treatment for rashes is strongly recommended to minimize the duration and severity of the adverse event.

On day 1 of treatment with selumetinib:

- Recommend to use skin moisturizer (alcohol free) at bedtime.
- Avoid excessive exposure to sunlight. Use sunglasses and sunscreen.
- Use of topical retinoids or benzoyl peroxide is not recommended.

For adults with grade 1 rash: Apply a mild / moderate strength topical steroid and/or topical antibiotic.

For adults with grade 2 rash: Apply a moderate strength topical steroid and consider an oral antibiotic.

For adults with ≥ grade 3 rash or a grade 2 rash considered to be intolerable: Hold selumetinib. Apply moderate strength topical steroid and consider an oral antibiotic. If an infection is suspected, consider other broad-spectrum antibiotic cover. Also consider referral to a dermatologist (and manage rash per recommendation). If rash improves to grade 2 or less, restart selumetinib at reduced dose.

For both adult and pediatric subjects, the following guidelines have been found to be useful:

Acneiform rash:

Experience with acneiform rash in the pediatric studies to date suggests that topical clindamycin gel or lotion applied BID, rather than steroids, is the most helpful for pustular rash (typically seen in the older child/adolescent). In severe cases, semisynthetic oral tetracyclines such as doxycycline or minocyline may also be useful for older children and adolescents, but should be avoided in children younger than 8 years old because of risk to tooth development.

Eczematous rash/xerosis:

Eczematous/dry skin rash and other macular (non-acneiform) rash should be treated with a moisturizer such as Cerave or Eucerin. A low potency topical steroid may also be used if symptomatic. Ketoconazole shampoo should be used for any rash involving the scalp.

Paronychia:

For patients who do not undergo drainage, silver nitrate may be used, as well as topical bactroban, steroids, and/or antifungals. Silver nitrate is only of value when there is open inflamed skin or granulation tissue (e.g. pyogenic-granuloma-like lesions). If the periungual skin is swollen but intact (whether infectious or non-infectious), silver nitrate is not recommended. Patients should be cautioned to avoid trauma to the area. Podiatry consult may be considered for partial nail removal.

Patients who undergo incision and drainage and are found to have no infectious organisms on culture, should be treated as above. If infection is identified, patients may be treated with systemic antibiotics (oral tetracyclines).

If paronychia recurs or develops in other fingers or toes, Flurandrenolide (e.g. Cordran) tape or topical steroid cream such as triamcinolone can be used in the morning and Bactroban and Nizoral topical ointments in the evening.

Oral Care:

Prevention, early diagnosis and management of stomatitis may reduce the need for dose interruption and / or reductions of the study medications due to severe stomatitis and so allow the patient to continue on the study drugs. It is strongly recommended that patients receive advice regarding daily oral health care regimes, both before and during treatment.

Patients with a healthy mouth may use non-alcoholic mouthwash several times (4 to 6 times daily, or according to the instructions) daily, e.g. after each meal, during the study. Saline mouthwashes (Sodium chloride 0.9%) should be preferred in cases of stomatitis, and should be used at a different time to toothbrushing, e.g. after tea.

Use of a mouthwash immediately after selumetinib intake is recommended.

The tongue can be gently brushed (if not sore) with a soft toothbrush.

Patients with, or at risk of stomatitis should not use commercial / over-the-counter mouthwashes because of the alcohol content and astringency. Chlorhexidine mouthwashes are not recommended for the treatment of established stomatitis.

The mouth should be regularly inspected by the patient and healthcare professionals.

Smoking should be strongly discouraged; patients should be offered help with smoking cessation if necessary in the form of nicotine replacement therapy or referral to smoking cessation services.

A high alcohol intake should be discouraged and patients advised to avoid painful stimuli such as spicy foods, hot food and drink.

Teeth should be brushed twice daily with a fluoride toothpaste and soft toothbrush, in the morning before breakfast and last thing in the evening before bed, about 30 minutes after eating. Toothbrush should be replaced regularly at least every 3 months but patients with stomatitis should change their toothbrush every 4 - 6 weeks.

[figure not shown]
- Use of soft toothbrush is recommended
- Dental floss should be used once daily (caution in patients with coagulopathies including a low platelet count)

In the event of sore mouth or stomatitis:

- Consider treating stomatitis at an early stage (CTCAE grade 1) or as soon as the patient complains of a sore mouth.
- Consider using oral topical analgesic anaesthesia with or without topical steroids,

antiviral and/or antifungal medications depending on the patient's clinical condition and the local standard medical practice.

5.4.5 Elevated CPK: To reduce possible consequences associated with CK elevation that may be arising from a muscular source, the management guideline described below should be followed:

* Muscular weakness, pain or tenderness

Version 3.0 12-Sept-2013

5.4.6 Pneumocystis jiroveci pneumonia (PJP) prophylaxis

The use of medication (i.e., Bactrim) for PJP prophylaxis in patients is recommended, but is at the investigator's discretion.

5.4.7 Neurosurgical Procedures

If a neurosurgical procedure is required for a reason other than tumor progression (i.e. the onset of hydrocephalus), these procedures should be documented, but will not constitute criteria for declaring the patient "off therapy". Given the potential for the drug to affect wound healing, selumetinib should be held until the patient is clinically stable and has recovered from the acute effects of surgery.

5.4.8 Concomitant Therapy

Other anti-cancer or experimental agents are not permitted.

5.5 Duration of Therapy

In the absence of treatment delays due to adverse event(s) or disease progression, treatment may continue for 26 courses (approximately two years) or until one of the Off Treatment Criteria found

in Section 5.6 applies.

During the second year of treatment, procedures consistent with good clinical care will continue. Patients will be seen monthly for medical history, physical exam (including height, weight, vital signs, and performance status), neurologic exam, dates of drug administration, relevant laboratory evaluations and routine neuro-imaging assessments. Therapy-related events will be recorded per standard assessments, including adverse events, date of disease progression, date of last follow up, date patient goes off treatment and date off study. Please review the table in Section 10 of the protocol for the required assessments and intervals. All patients must discontinue treatment with selumetinib following the completion of 26 courses of treatment.

5.6 **Duration of Follow Up**

Discontinuation of Treatment

At the discontinuation of treatment, the "Off Treatment Date" is to be recorded in the CRF and is to be consistent with the reason given for going off treatment. The "Last Treatment Date" is defined as the last date that the patient received protocol based therapy. Date of "off treatment" must be the greatest of the date of last treatment, date of procedure, date of patient assessment, notification of patient/family decision, or decision made by the physician that resulted in the patient being taken off protocol treatment. The reason for discontinuation of treatment must be documented by the attending investigator in the medical record and recorded in the CRF. The "Off Treatment Date" and the "Last Treatment Date" should be the same for patients that complete all protocol defined treatment.

Patients will be considered Off Treatment for the following reasons:

- 5.6.1 Development of unacceptable toxicity as outlined in Section 5.2.1 that does not resolve within 14 days.
- 5.6.2 Non-compliance with study guidelines
- 5.6.3 Progressive disease, as outlined in section 11.1 and 11.2
- 5.6.4 Development of a medical or psychiatric illness, that in the investigator's judgment renders the patient incapable of further therapy on this protocol
- 5.6.5 The patient, parent or legal guardian refuses further treatment on this protocol
- 5.6.6 Pregnancy
- 5.6.7 Completion of maximum number of courses of treatment with selumetinib

Patients will be monitored every 6 months for 2 years after protocol treatment. Ongoing AE's should be monitored as per section 7.4.3. Additionally, patients will be followed for initiation of subsequent therapy for NF2, selumetinib related adverse events (including cardiac toxicities), date of disease progression, date of last follow up, and date of death.

Patients who are off protocol therapy must be followed until an Off Study Criterion is met. Ongoing AE's should be monitored as per section 7.4.3.

5.7 Criteria for Removal from Study

The date and reason for the patient coming off study must be documented in the CRF.

- 5.7.1 Patient determined to be ineligible (Treatment with selumetinib was never started).
- 5.7.2 Patient determined to be ineligible (Treatment with selumetinib WAS started).

These patients must be observed for 30 days following date deemed ineligible. All AE's must be recorded in that 30-day period.

- 5.7.3 Patient, parent, or guardian withdraws consent for continued participation.
- 5.7.4 Patient death while on study. The IRB, Sponsor, and FDA must be notified as per Section 7
- 5.7.5 Patients removed from treatment for progressive disease (PD) be observed for 30 days following last dose of selumetinib.
- 5.7.6 Commencement of additional anti-cancer therapy
- 5.7.7 Completion of protocol defined follow up

6 DOSING DELAYS/ DOSE MODIFICATION

6.1 Notification of Study Chair

[figure not shown]
The study chair or co-chair must be notified of any dosage modifications, prior to the implementation of the dose modification

6.2 Hematologic and Non-Hematologic Adverse Events and Management

Table 7

Event	AE Grade or Observation	Dose Modification
Dermatology/Skin	Grade 1 or 2	Maintain dose
	Intolerable Grade 2;	Hold selumetinib until ≤ tolerable grade 2;
		reduce one dose level and resume
	Grade 3 or 4	treatment. Skin care guidelines are located
		in Section 5.4.4.
	Grade 4	Patients with grade 4 rash (i.e. life
		threatening generalized exfoliative
		ulceration; erythemia multiforme/toxic
		epidermal necrolysis should be removed
		from study. Skin care guidelines are located in Section 5.4.4
		located in Section 5.4.4
Diarrhea (if anti-diarrheal	Grade 1 or 2	See algorithm and guidelines in Section
treatment is ineffective)		5.4.3.
	Grade 3 or 4	See algorithm and guidelines in Section
	Grade 5 of 4	5.4
		Hold selumetinib until = tolerable grade</td
		2, on loperamide. Reduce 1 dose level and
		resume treatment.
Visual Disturbances - for	Grade 1 or 2	Hold selumetinib until Eye exam is
any new or progressive		completed; If the Ophthalmology exam is
vision problem(including		normal and the toxicity resolves within
but not limited to the		24hrs or an alternate cause for the vision problem is identified – restart selumetinib
following)		at the same dose level. See algorithm in
Blurred Vision, Flashing		5.4.1
Lights, Floater, Photophobia		
	Grade 3 or 4	Hold selumetinib until Eye exam is
		completed; If alternate etiology for vision
		change is identified, contact study chair to
		discuss restarting of selumetinib. See
		algorithm in 5.4.1
Hematologic	Grade 1, 2, or 3	Maintain dose
With the exception of	Grade 3 thrombocytopenia	Hold selumetinib until < grade 2, then
		· · · · · · · · · · · · · · · · · · ·

lymphopenia	associated with bleeding	reduce 1 dose level and resume treatment.
	Grade 4	Hold selumetinib until < grade 2, then reduce 1 dose level and resume treatment.
Liver Function	Grade 1 or 2	Maintain dose
Serum bilirubin, AST, ALT	Grade 3	Hold selumetinib. If returns to levels meeting eligibility criteria within 7 days, then restart at the same dose.
	Grade 3 that does not return to meet eligibility criteria within 7 days, or Grade 4	Hold selumetinib until < grade 2, then reduce 1 dose level and resume treatment.
Other non-hematological toxicity	Grade 1 or 2	Maintain dose
·	Grade 2 of concern (e.g., pulmonary, neurotoxicity, or intolerable stomatitis)	
	Grade 2 that persists for >7 days and is considered sufficiently medically significant or intolerable by patients as to warrant treatment interruption and /or dose modifying	Hold selumetinib until < grade 2, then reduce 1 dose level and resume treatment.
	Grade 3 or 4	Hold selumetinib until < grade 1, then reduce 1 dose level and resume treatment.

[figure not shown]

Version 3.0 12-Sept-2013

Cardiac Function: Please see algorithm below

Management of Asymptomatic Left Ventricular Ejection Fraction (LVEF) Reduction

* Muscular weakness, pain or tenderness

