5 TREATMENT PLAN

Treatment will be administered on an outpatient basis. Reported adverse events and potential risks are described in Section 7. Appropriate dose modifications are described in Section 6.2. No investigational or commercial agents or therapies other than those described below may be administered with the intent to treat the patient's tumor.

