5.2 Dose Modifying Toxicities (DMT)

Toxicities will be graded according to CTCAE version 5.0 of the NCI Common Terminology Criteria for Adverse Events. CTCAE version 5.00 is identified and located on the CTEP website at http://ctep.cancer.gov/protocolDevelopment/electronic_applications/ctc.htm. All appropriate treatment areas should have access to a copy of CTCAE version 5.0.

DMT will be defined as any of the events listed in this section that are at least possibly related to the investigational agent that occur regardless of expectedness. Please consult Table 7 for appropriate dose modifications.

- 5.2.1 The following are Dose-Modifying Toxicities (DMT's)
 - Any selumetinib-related adverse event that results in a delay of treatment > 7 days
 - Non-hematologic dose modifying toxicity is defined as:
 - o Any grade 4 non hematologic toxicity
 - o Any grade 3 non-hematologic toxicity with the exception of:
 - Grade 3 nausea and vomiting of < 3 days
 - Grade 3 asymptomatic elevation of transaminases that returns to levels meeting eligibility criteria within 7 days of study drug interruption and does not recur upon restarting drug
 - Grade 3 fever or infection if fewer than 3 days in duration
 - Grade 3 asymptomatic hypophosphatemia, hypokalemia, hypocalcemia or hypomagnesemia responsive to oral supplementation

- Grade 3 asymptomatic elevation of CPK
- Any grade 2 non-hematological toxicity that persists for more than 7 days and is considered sufficiently medically significant or sufficiently intolerable by patients as to warrant treatment interruption and/or dose reduction will be considered dose-modifying.
- Hematologic dose modifying toxicity is defined as:
 - o Any grade 4 hematologic toxicity with the exception of lymphopenia
 - o Grade 3 thrombocytopenia with bleeding

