6.2.1 Criteria for continued treatment after toxicity

The study chair or co-chair must be notified of any dosage modification prior to the implementation of the dose modification.

Dose de-escalations to dose level -1 are permitted. See Appendix D.

All patients who require dose de-escalation from dose level -1 must be taken off treatment.

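### A grade 4 rash that improves meets two opposite rules: Table 7 both resumes selumetinib one dose level lower and removes the patient, and Section 5.4.4 repeats the restart for adults

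*Combined protocol and SAP*

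**What the plan says.** Three instructions apply to a grade 4 rash once it has improved.

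- **Table 7, Dermatology/Skin, row for intolerable grade 2 and grade 3 or 4 (Section 6.2).** Hold until the event is a tolerable grade 2 or lower, then "reduce one dose level and resume" treatment.
- **Table 7, Dermatology/Skin, next row, grade 4.** The row opens "Patients with grade 4 rash (i.e. life", goes on to describe life-threatening forms, and ends its list with "epidermal necrolysis should be removed" from study.
- **Section 5.4.4, adults.** "For adults with ≥ grade 3 rash or a grade 2 rash considered to be intolerable: Hold selumetinib". Then, after advice on topical and antibiotic care: "If rash improves to grade 2 or less, restart selumetinib at reduced dose".

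On precedence, Section 5 says "Appropriate dose modifications are described in Section 6.2" and Section 5.2 says "Please consult Table 7 for appropriate dose modifications". Section 6.2.1 adds "All patients who require dose de-escalation from dose level -1 must be taken off treatment".

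**The concern.** All the rules stop the drug first, so the acute management is not in doubt. The difficulty comes after recovery. An investigator whose patient has recovered from a grade 4 rash can find one instruction to restart and another to remove, in adjacent rows of the same table. For an adult, the supportive-care text also says restart.

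What is at stake is re-exposure after a skin reaction that the protocol's own description extends to toxic epidermal necrolysis. The unsafe action would not be a deviation: an investigator could take it in good faith by following a stated rule. The skin rules will be used in practice. Section 2.1.2 lists rash among the dose-limiting toxicities of the pediatric phase 1 study at 25 mg/m² twice daily, which is this trial's dose.

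**Working it through.** The main check is a comparison of text. The case considered is a patient at dose level 0 with a grade 4 rash that falls to a tolerable grade 2 or lower within 14 days.

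| Place | Does it cover grade 4 rash? | Action after improvement |
|---|---|---|
| Table 7, intolerable grade 2 and grade 3 or 4 row | Yes, grade 4 is named | Resume one level lower |
| Table 7, grade 4 row | Yes | Remove from study |
| 5.4.4, adults | Yes, grade 3 or higher | Restart at reduced dose |

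**Does another section settle it?**

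1. Sections 5 and 5.2 point to Section 6.2 and Table 7 for dosing. That ranks Table 7 above 5.4.4 but leaves the two Table 7 rows in conflict.
2. Section 5.2.1 makes any grade 4 non-hematologic toxicity dose-modifying. It does not say whether treatment may resume.
3. Section 5.3 allows a new course once a rash is back to tolerable grade 2 or baseline, with no grade 4 exception. It is permissive only, so it is secondary support.
4. Section 5.6.1 ends treatment if the toxicity has not resolved within 14 days. It does not reach a rash that resolves in time. A strict reading of resolution would remove more cases.
5. Section 5.6.4 allows the investigator to stop on judgment. Neither 5.6 nor 5.7 lists grade 4 rash.
6. Section 6.2.1 takes off treatment anyone at dose level -1 who needs a further reduction. The conflict is therefore confined to dose level 0.

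**Scale**

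- Planned maximum: two strata of 9 + 8 = 17 patients (Section 13.2), so 2 × 17 = 34.
- Pediatric phase 1 at this dose (Section 2.1.2): 3 of 12 patients aged 12 or over had a dose-limiting toxicity of any type. Grades are not given, so this does not estimate grade 4 rash.
- Adult capsule phase 1 (Section 2.2.2): the only grade 4 event was hypoglycemia, so there were 0 grade 4 rashes. The text uses a denominator of 56, but the listed cohorts sum to 6 + 7 + 7 + 8 = 28, so both are shown.
- Exact one-sided 95% upper limit for zero events in n patients: 1 − 0.05^(1/n). For n = 56: 1 − 0.05^(1/56) = 5.2%. For n = 28: 1 − 0.05^(1/28) = 10.1%.

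Those were adult flat doses, so the limits are context only. They show that the data are too few to rule the event out, not how often it will occur here.

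**The case against.** The best case for leaving the text alone is that Table 7 works by carve-out. Elsewhere a broad row is followed by a narrower one that overrides it without saying so: hematologic grades 1 to 3 keep the dose, and the next row then holds it for grade 3 thrombocytopenia with bleeding. Read that way, the grade 4 row is simply the exception. The two skin rows may also differ in scope, since only the later one speaks of rash, leaving the earlier row to cover other grade 4 skin events. The table text was damaged in extraction, so cell boundaries are uncertain. Section 5.4.4 is supportive-care guidance, and Table 7 cites it only for skin care. Finally, Sections 6.1 and 6.2.1 require the study chair or co-chair to be told before any dose change, and Section 12.4 provides real-time review of dose-modifying toxicities.

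Much of this stands. The carve-out is the sensible reading, and the fix adopts it. Chair notification and review do lower the chance of error. But the conflict remains:

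- The resume row names grade 4 itself and is not limited to events other than rash. No text states the exception.
- Section 5.4.4 is intact running prose. Its grade 3 or higher wording conflicts with the removal row whatever the table layout, and the grade 4 row itself sends the reader there for skin care.
- The life-threatening forms in the grade 4 row are introduced as an explanation of grade 4 rash. Even if they were meant as a subset, those events are still grade 4 and still fall under both restart instructions.
- Notification tells the chair that a change is planned. It does not say which rule governs.

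**Conclusion.** The contradiction holds as written and should be fixed. For a patient at dose level 0 whose grade 4 rash improves within 14 days, one Table 7 row directs resumption and the next directs removal; for adults, 5.4.4 sides with resumption. The conclusion rests on the ordinary meaning of the grade labels and of the 5.4.4 text. The 5.4.4 part does not depend on how the table was laid out.

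The size is small. The event is probably rare and its rate in this population is not given. The affected group is a subset of at most 34 patients, further reduced by 5.6.1, 5.6.4 and 6.2.1. The matter is worth correcting because the consequence could be severe for the individual patient.

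The Simon design figures and evaluability for response are untouched. No loss of follow-up is implied: 5.7 has no toxicity criterion, 5.6 keeps off-treatment patients under observation, and 7.4.3 follows related events to resolution or stability. The grade 4 row's reference to leaving the study is only a mismatch with the off-treatment and off-study terms of 5.6 and 5.7.

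**What to change.** Follow the protocol's own grade 4 row, subject to confirmation by the sponsor's clinicians.

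1. In Table 7, limit the hold, reduce and resume row to intolerable grade 2 and grade 3. Either let the grade 4 row cover all grade 4 skin toxicity, or state the action for grade 4 skin events other than rash, for example by pointing to the grade 3 or 4 row under other non-hematological toxicity. No grade 4 skin event should be left without a row.
2. In 5.4.4, limit the restart sentence to grade 3 or intolerable grade 2 rash.
3. Add grade 4 rash to the off-treatment criteria in 5.6, with a matching exception in 5.3.
4. In the grade 4 row, say that the patient comes off treatment rather than off study, so that it matches 5.6 and follow-up clearly continues.

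Items 1 and 2 remove the conflict; items 3 and 4 bring the rest of the protocol into line. The cost is wording edits in four places, with no change to sample size, visits or data collection.

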3.1.10 Organ Function Requirements

3.1.10.1 Adequate Bone Marrow Function Defined as:

- Peripheral absolute neutrophil count (ANC) $\geq 1500/\mu L$
- Platelet count $\geq 100,000/\mu L$ (transfusion independent, defined as not receiving platelet transfusions within a 7 day period prior to registration)
- Hemoglobin ≥ 9 g/dL (may receive RBC transfusions)

3.1.10.2 Adequate Renal Function Defined as:

- Creatinine clearance or radioisotope GFR ≥ 70ml/min/1.73 m2 or
- A serum creatinine ≤1.5×ULN for age and sex

3.1.10.3 Adequate Liver Function Defined as:

- Bilirubin (sum of conjugated + unconjugated) ≤ 1.5 x upper limit of normal (ULN) for age
- AST(SGOT)/ALT(SGPT) ≤2.5×ULN institutional upper limit of normal for age

3.1.10.4 Central Nervous System Function:

- Patients with seizure disorder may be enrolled if they are receiving non-enzyme inducing anticonvulsants and the seizures are well controlled.

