5.3 Criteria for starting subsequent courses

A course may be repeated every 28 days if the patient has at least stable disease and the patient meets the following criteria within seven days of the start of each course:

- ANC $\geq 1,000/\mu L$
- Platelets $\geq 100,000/\mu L$
- Non-hematologic dose modifying toxicity related to selumetinib recovered to < grade 2 or baseline (for rash or diarrhea: tolerable grade 2 or baseline)
- No evidence of progressive disease

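### The Table 7 liver row drops the recurrence condition of section 5.2.1, so a grade 3 AST/ALT rise that recurs on restarting and again recovers within 7 days is, read literally, restarted at the same dose

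*Combined protocol and SAP*

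**What the plan says.** Section 5.2 defines dose-modifying toxicities as listed events at least possibly related to selumetinib, and directs the site onward: "Please consult Table 7 for appropriate dose modifications". Under 5.2.1 any grade 3 non-hematologic toxicity is dose-modifying unless an exception applies. The exception relevant here is "Grade 3 asymptomatic elevation of transaminases that returns to levels meeting eligibility criteria within 7 days of study drug interruption and does not recur", where the clause in full ends "does not recur upon restarting drug".

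Table 7 in section 6.2 has a separate row for liver function, covering bilirubin, AST and ALT. Grades 1 and 2 keep the dose. For grade 3 the action is "Hold selumetinib. If returns to levels meeting eligibility criteria within 7 days, then restart at the same dose". The dose is reduced by one level only for "Grade 3 that does not return to meet eligibility criteria within 7 days, or Grade 4".

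For AST/ALT, the eligibility level in section 3.1.10.3 is "AST(SGOT)/ALT(SGPT) ≤2.5×ULN institutional upper limit of normal for age".

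**The concern.** The same-dose line in Table 7 and the exception in 5.2.1 describe nearly the same event, but the table stops at recovery within 7 days and says nothing about a repeat. Recurrence when the drug is given again is exactly the feature for which 5.2.1 withdraws the exemption. The action table nevertheless gives a repeat event the same response as a first one.

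Two things are at stake. The first is patient safety: the patient goes back to a dose at which the rise has already come back once. The second is consistency: one treating investigator may reduce the dose because of the 5.2.1 label, while another follows the Table 7 row and does not.

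**Working it through.** The main check is a comparison of rules. The plan gives no figure of its own to reproduce on this point.

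**Step 1. Follow one patient through the text.** Assume the rise is asymptomatic and at least possibly related to selumetinib.

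| Event | Status under 5.2.1 | Table 7 liver row |
|---|---|---|
| First grade 3 AST/ALT rise, at or below 2.5 × ULN within 7 days of the hold | Exempt, provided it does not recur on restarting | Hold, then same dose |
| Grade 3 rise recurs on restarting, again at or below 2.5 × ULN within 7 days | Dose-modifying (exemption lost) | Hold, then same dose |
| Grade 3 rise not recovered within 7 days, or grade 4 | Dose-modifying | Hold, then reduce one level |

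In the second line the status changes but the dose action does not.

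**Step 2. Look for another rule that sets a dose for the second line.**

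- 5.2.1, delay bullet: "Any selumetinib-related adverse event that results in a delay of treatment > 7 days". An event that recovers and restarts within 7 days does not meet it.
- 5.3: the next course requires "Non-hematologic dose modifying toxicity related to selumetinib recovered to < grade 2 or baseline" (with an allowance for rash and diarrhea). This governs when a course may start, not the dose.
- 5.6.1: off treatment depends on failure to resolve within 14 days, not on recurrence.
- 6.1: the study chair must be told before a dosage modification. No dose is specified.
- 6.2, Table 7, other non-hematological toxicity: grade 3 or 4 leads to a one-level reduction, but liver tests have their own row.
- 6.2.1 and Appendix D: these state what a reduction is and that a patient needing a further one from level -1 stops treatment. They apply only once a reduction has been triggered.

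Some figures are missing from the available text. The liver row refers to no algorithm, and the captions that survive near Table 7 concern LVEF and muscle symptoms, so a liver recurrence rule in a missing figure is unlikely.

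**Step 3. Size of the difference.** Inputs are the Appendix D morning plus evening doses. Change = (level -1 total − level 0 total) / level 0 total.

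| BSA (m²) | Level 0, mg/day | Level -1, mg/day | Change |
|---|---|---|---|
| 0.55–0.69 | 10 + 10 = 20 | 10 + 0 = 10 | −10/20 = −50.0% |
| 0.70–0.89 | 20 + 20 = 40 | 20 + 10 = 30 | −10/40 = −25.0% |
| 0.90–1.09 | 25 + 25 = 50 | 25 + 10 = 35 | −15/50 = −30.0% |
| 1.10–1.29 | 30 + 30 = 60 | 25 + 20 = 45 | −15/60 = −25.0% |
| 1.30–1.49 | 35 + 35 = 70 | 25 + 25 = 50 | −20/70 = −28.6% |
| 1.50–1.69 | 40 + 40 = 80 | 30 + 30 = 60 | −20/80 = −25.0% |
| 1.70–1.89 | 45 + 45 = 90 | 35 + 30 = 65 | −25/90 = −27.8% |
| 1.90 and above | 50 + 50 = 100 | 35 + 35 = 70 | −30/100 = −30.0% |

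The same-dose line gives a change of 0% in every band.

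**Step 4. Frequency.** The expected-events table in section 7 places ALT/AST increase in the band from 3% to below 20% and states no grade. It says nothing about recurrence on restarting, so the number of patients affected cannot be derived.

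**The case against.** The strongest reply is that the two sections can be read together. The same-dose line tracks the 5.2.1 exception so closely that a site would take it as the action for the exempt event only. 5.2.1 also accepts interruption as one form of dose modification for some grade 2 events, so the hold is itself a response to a recurrent event. This stands in part: the sections do not strictly contradict each other, because 5.2.1 classifies events and orders no reduction. But if the same-dose line is reserved for exempt events, no line in the liver row covers the recurrent one.

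The second reply is that safeguards exist. Section 12.4 provides real-time study chair review of dose-modifying toxicities, section 12.3 provides DSMB review, and 5.6.4 leaves room for the investigator's judgement. A hold can reasonably be read as a dosage modification that requires prior notice under 6.1. Section 7.4.3 follows related events until they return to baseline; if that meaning of resolution is carried into 5.6.1, a patient still above baseline at 14 days would stop treatment. Section 7 also leaves event management to local practice. All of this makes unnoticed repeated rechallenge unlikely. None of it states which dose to resume.

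A reader might go further and infer that the wording permits a countable number of same-dose restarts, one for each pre-course liver test. The documents do not support such a figure. Note B of the study calendar allows more frequent testing, so the schedule sets no ceiling, and no recurrence rate is given. A reader might also treat the row's inclusion of bilirubin, or its silence on symptoms, as errors. Both may be deliberate, and the point does not depend on them.

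**Conclusion.** The point holds as a narrow gap between two dosing rules. For an at least possibly related grade 3 AST/ALT rise that recurs on restarting and again recovers within 7 days, the protocol classes the event as dose-modifying while its action table, followed literally, leaves the dose unchanged. Where it applies, the consequence is one dose level, as tabulated above.

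The conclusion rests on three assumptions: that the liver row, not the row for other toxicities, governs AST/ALT; that return to eligibility levels counts as recovery; and that no missing figure contains a liver recurrence rule. The near-identical wording suggests an omitted clause, but intent cannot be shown.

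This is a patient-safety wording matter that is worth amending. It does not touch the Simon two-stage design, its error rates or either primary endpoint.

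**What to change.** Make two changes in the Table 7 liver row:

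1. For AST/ALT, limit the same-dose restart to a grade 3 elevation that has not recurred on restarting the drug.
2. Add to the triggers of the row's existing line (hold until below grade 2, then reduce one level): *at least possibly related grade 3 AST/ALT elevation that recurs upon restarting drug*. Section 6.2.1 then applies as it stands if the patient is already at level -1.

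Keep both the relatedness condition and the link to restarting. Without them, an unrelated rise, or an isolated one many courses later, could force a reduction that 5.2.1 does not call for. A cap on same-dose restarts per patient would go beyond 5.2.1 for the same reason. If the sponsor does intend repeated same-dose restarts, it should say so in 5.2.1 so that the two sections agree.

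The cost is a wording amendment to one table row. It needs no extra patients, visits or tests, since AST/ALT is already measured before each course (section 10). The downside is an occasional one-level reduction, or a treatment stop for a patient already at level -1, because of laboratory changes that reverse quickly on a hold. That cost is real in a disease for which section 3.1.5 says there is no standard effective chemotherapy.
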